10. STUDY CALENDAR

Tumor tissue for the mesothelin expression assay is mandatory at pre-registration to establish eligibility for Phase 2 subjects. Pre-study evaluations are to be conducted within 14 days of registration unless stated otherwise. An ophthalmological exam is to be conducted within 28 days prior to the start of protocol therapy. Scans and x-rays must be done < 4 weeks prior to the start of therapy. Windows of \pm 1 to 2 days are permissible for cycles 1, 2 and 3; windows of \pm 3 days are permissible for cycles 4 and beyond. In the event that the patient's condition is deteriorating, laboratory evaluations should be repeated within 48 hours prior to initiation of the next cycle of therapy.

	Pre-registration (Phase 2 only)	Pre-study	Cycle 1			Cycle 2			Cycle 3			Cycle 4 and higher			Off Study ^k
			Wk 1	Wk 2	Wk 3	Wk 4	Wk 5	Wk 6	Wk 7	Wk 8	Wk 9	Wk 10	Wk 11	Wk 12	
Anetumab raptansine			A			A			A			A			
Pembrolizumab			B			B			B			B			
Informed consent		X													
Concurrent meds		X	X-----X												
Physical exam ^a		X	X			X			X			X			X
Ophthalmologic exam ^b		X				X			X			X			
Performance status		X	X			X			X			X			X
CBC w/diff, plts		X	X	X	X	X	X	X	X	X	X	X			X
Serum chemistry ^c		X	X	X	X	X	X	X	X	X	X	X			X
TSH, T3, T4 ^d		X	X			X			X			X			X
PT/INR, aPTT		X													
Serum pregnancy ^e		X													
ECG		X				X			X			X			

	Pre-registration (Phase 2 only)	Pre-study	Cycle 1			Cycle 2			Cycle 3			Cycle 4 and higher			Off Study ^k
			Wk 1	Wk 2	Wk 3	Wk 4	Wk 5	Wk 6	Wk 7	Wk 8	Wk 9	Wk 10	Wk 11	Wk 12	
Echo or MUGA ^f		X													
Adverse event evaluation			X-----												X
Radiologic evaluation/ Tumor measurements		X	Radiologic evaluation and tumor measurements are performed at the end of cycle 3/before cycle 4 begins and every 3 cycles thereafter. Documentation (radiologic) must be provided for patients removed from study for progressive disease.												X
Tissue for mesothelin assay ^g	X	X													
Tissue for PD-L1 assay ^h		X													
Blood for PKs and correlative studies ⁱ		X	X	X		X			X	X		X			
PRO-CTCAE ^j			X	X	X	X	X	X	X	X	X				X

A: Anetumab Ravtansine: ***For all phase 1 and phase 2 group 2 patients:*** Dose as determined by the phase 1 study by IV infusion over 60 minutes on day 1 of each cycle for up to 12 months total. Anetumab ravidansine is to be administered prior to pembrolizumab.

B: Pembrolizumab: 200 mg by IV infusion over 30 minutes on day 1 of each cycle for up to 24 months total for all groups.

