11.1.1 Schedule of Evaluations

For the purposes of this study, patients should be re-evaluated for response every 9 weeks. In addition to a baseline scan, confirmatory scans should also be obtained 4-6 weeks following initial documentation of objective response.

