11.1.6 Duration of Response

Duration of Overall Response: The duration of overall response is measured from the time measurement criteria are met for CR or PR (whichever is first recorded) until the first date that progressive disease is objectively documented (taking as reference for progressive disease the smallest measurements recorded since the treatment started).

The duration of overall CR is measured from the time measurement criteria are first met for CR until the first date that progressive disease is objectively documented.

Duration of Stable Disease: Stable disease is measured from the start of the treatment until the first date that progressive disease is objectively documented taking as reference the smallest measurements recorded since the treatment started, including the baseline measurements.

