13.5 Analysis of Secondary Endpoints

13.5.1 Duration of Response

Duration of response is defined for all evaluable patients who have achieved a response as the date at which the patient's objective status is first noted to be a PR or CR to the earliest date progression is objectively documented. If a patient has not had disease progression, they will be censored on the date of their last disease assessment. The distribution of duration of response will be estimated using the method of Kaplan-Meier. The comparison of duration of response between two treatment arms will be based on the log-rank test. This calculation will start with the date of start of treatment.

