13.5.2 Overall Survival

Overall survival is defined as the time from the start of treatment to death due to any cause. The distribution of survival time will be estimated using the method of Kaplan-Meier. The comparison of overall survival between two treatment arms will be based on the log-rank test.

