13.5.3 Progression Free Survival

Progression free survival is defined as the start of treatment to the earliest date that

disease progression is objectively documented or death due to any cause. The distribution of progression-free survival will be estimated using the method of Kaplan-Meier. The comparison of progression-free survival between two treatment arms will be based on the log-rank test.

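### Section 13.5.1 gives duration of response two start dates: first PR or CR, as in 11.1.6, and the start of treatment.

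*Combined protocol and SAP*

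**What the plan says.** Section 13.5.1 applies to evaluable patients who achieve a response. Its first sentence runs the interval from the date on which "objective status is first noted to be a PR or CR to the earliest date progression is objectively documented". Patients without progression are censored at their last disease assessment, the distribution is estimated by Kaplan-Meier, and the arms are compared by the log-rank test. The last sentence of the paragraph then reads "This calculation will start with the date of start of treatment".

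The response section supports the first of these. Section 11.1.6 says that the duration of overall response is "measured from the time measurement criteria are met for CR or PR (whichever is first recorded"), up to the first objectively documented progression. That sentence also mentions the start of treatment, but only to fix which smallest measurement is the reference for judging progression. It does not set the start of the interval.

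Treatment start is the stated clock for three other measures:

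- Stable disease, 11.1.6: "Stable disease is measured from the start of the treatment until the first date that progressive disease is objectively documented".
- Overall survival, 13.5.2: "Overall survival is defined as the time from the start of treatment to death due to any cause".
- Progression-free survival, 13.5.3: "Progression free survival is defined as the start of treatment to the earliest date that" progression is documented, or death.

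**The concern.** One interval cannot have two origins. Under the first sentence of 13.5.1 the quantity is how long a response lasts. Under the last sentence it is time to progression, counted from first dose, in the subset of patients who responded. The second quantity includes a stretch before any response existed, so it is longer for every responder.

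Two results are exposed. The Kaplan-Meier curve and its median move to longer times, which matters when the figure is set beside response durations measured from response in other studies. The between-arm comparison would also mix time to response with durability: an arm that responds later would gain apparent duration for that reason alone. If the origin is left open, it may be settled after the data have been seen.

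**Working it through.** **The texts side by side**

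| Place | Quantity | Start |
|---|---|---|
| 13.5.1, first sentence | Duration of response | First PR or CR |
| 13.5.1, last sentence | The same calculation | Start of treatment |
| 11.1.6 | Duration of overall response | CR or PR criteria first met |
| 11.1.6 | Stable disease | Start of treatment |
| 13.5.2 | Overall survival | Start of treatment |
| 13.5.3 | Progression-free survival | Start of treatment |

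Three readings might rescue the closing sentence, and none does.

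1. It refers only to the log-rank test in the sentence before it. The endpoint would then be defined from first response but compared from first dose, which is still two clocks for one endpoint.
2. It is a stray sentence meant for overall or progression-free survival. Each of those states its own start, so nothing depends on it.
3. It defines a second, intended measure. No such measure is named or defined.

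**Size of the discrepancy**

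The plan states no figure for duration of response, so there is none to reproduce. The offset follows from the scan schedule.

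- Study calendar (section 10): "Radiologic evaluation and tumor measurements are performed at the end of cycle 3/before cycle 4 begins and every 3 cycles thereafter". Cycles last 21 days.
- Section 11.1.1: "patients should be re-evaluated for response every 9 weeks".
- First scan: 3 × 21 = 63 days = 9 weeks; 63 / 30.4375 = 2.07 months.
- Second scan: 6 × 21 = 126 days = 18 weeks; 126 / 30.4375 = 4.14 months.

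Reported duration = true duration + offset. Relative inflation = offset / true duration. The 6- and 12-month durations are assumptions. The 600 days comes from section 2.2.1, where four of five single-agent responses at the MTD lasted longer than that; so small a sample does not set this trial's median.

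| True duration | Response at first scan | Response at second scan |
|---|---|---|
| 6 months (assumed) | 8.07 months, +34.5% | 10.14 months, +69.0% |
| 12 months (assumed) | 14.07 months, +17.2% | 16.14 months, +34.5% |
| 600 days | 663 days, +10.5% | 726 days, +21.0% |

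**Effect on the log-rank test**

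If every responder responds at the same scan, the change is a constant shift and the test statistic is identical. If responders are split between scans in the same proportion in both arms, patients are re-ordered and the statistic changes, but neither arm is systematically favoured. If timing differs between arms, the comparison can be distorted.

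A simulation shows the range. The design rates give 49 × 0.20 = 9.8 and 49 × 0.40 = 19.6 responders, so 10 versus 20 were used. True durations were exponential and equal in both arms, with uniform censoring at 6 to 24 months, 5,000 replicates and a two-sided 5% level. All of these settings beyond the responder counts are assumptions, including the level, since 13.5.1 states none. Measured from response, the rejection rate was 5.1% to 6.4% throughout. Measured from treatment start, with one whole arm responding at the second scan and the other at the first, it was:

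| Median duration | Larger arm late | Smaller arm late |
|---|---|---|
| 6 months | 15.8% | 9.3% |
| 12 months | 9.5% | 5.7% |
| 600 days | 7.3% | 4.9% |

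With only half of one arm late, the rates ran from 4.6% to 8.2%. The effect therefore ranges from none to moderate, and the point does not depend on any one of these figures.

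**The case against.** The strongest reply is that the practical ambiguity is small. The opening of 13.5.1 is the only sentence there worded as a definition, and 11.1.6 independently gives the same origin. Against them stands one trailing sentence with an unclear referent. Most analysts would follow the definition, in which case nothing is inflated. The analysis covers only about 10 and 20 responders at the design rates. Duration of response is not among the objectives in section 1.2, and no decision rule is attached to it. Section 13.1.3.3 names it only as one unquantified consideration in a decision to terminate. The percentages rest mostly on assumed durations, and the one duration reported in the documents gives the smallest of them. Many of the simulated rejection rates lie close to the rates obtained from the correct origin.

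Most of this stands as a limit on weight. It does not remove the contradiction. The sentence is a complete, current instruction in the statistical section, and a programmer who carried it out would be following the plan. Duration of response has its own Kaplan-Meier estimate and between-arm test under 13.5, so the point is more than editorial.

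**Conclusion.** The concern holds. Section 13.5.1 contradicts itself and 11.1.6 on the start date, and nothing in the documents resolves it. If the closing sentence is followed, durations are nominally overstated by 63 days for a first-scan response and 126 days for a second-scan response. These offsets rest only on the scan schedule, with scans on time. The relative size depends on a true duration that is not known: over the values tried it runs from 10.5% to 69%. Any effect on the between-arm test depends on which arm responds later and by how much. If the first sentence is followed, there is no error in the result.

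This should be corrected before analysis. It does not touch the response-rate test, the futility boundary, the sample size or the power.

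**What to change.** Delete the closing sentence of 13.5.1. The endpoint, its Kaplan-Meier estimate and its log-rank comparison then all start when PR or CR is first noted, in agreement with 11.1.6. If time from treatment start to progression among responders is also wanted, define it separately under its own name.

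The cost is one sentence. No new data are needed and no other endpoint changes. If the closing sentence would have been followed, the reported duration becomes shorter.

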13.5.2 Overall Survival

Overall survival is defined as the time from the start of treatment to death due to any cause. The distribution of survival time will be estimated using the method of Kaplan-Meier. The comparison of overall survival between two treatment arms will be based on the log-rank test.

13.5.3 Progression Free Survival

Progression free survival is defined as the start of treatment to the earliest date that

disease progression is objectively documented or death due to any cause. The distribution of progression-free survival will be estimated using the method of Kaplan-Meier. The comparison of progression-free survival between two treatment arms will be based on the log-rank test.

13.5.4 Adverse Events

All eligible patients that have initiated treatment will be considered evaluable for assessing adverse event rate(s). The maximum grade for each type of adverse event will be recorded for each patient, and frequency tables will be reviewed for each arm to determine patterns. Additionally, the relationship of the adverse event(s) to the study treatment will be taken into consideration. The overall adverse event rates for Grade 3 or higher hematologic and non-hematologic adverse events at least possibly related to treatment will be compared between the two treatment groups using the Chi-square test (or Fisher's exact test if the data in the contingency table is sparse).

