3.3.11 Has a known history of Hepatitis B (defined as Hepatitis B surface antigen [HBsAg] reactive) or known active Hepatitis C virus (defined as HCV RNA [qualitative] is detected) infection.

Note: No testing for Hepatitis B and Hepatitis C is required unless mandated by local health authority.

3.3.12 Patients who are known to have a history of or a finding of corneal epitheliopathy at pre-study are excluded because anetumab ravidansine may worsen this condition and reduce vision.

3.3.13 Known additional malignancy that is progressing or requires active treatment. Exceptions include basal cell carcinoma of the skin, squamous cell carcinoma of the skin that has undergone potentially curative therapy, or *in situ* cervical cancer.

- 3.3.14 Receipt of transfusion of blood products (including platelets or red blood cells) or administration of colony stimulating factors (including granulocyte colony-stimulating factor [G-CSF], granulocyte macrophage colony-stimulating factor [GM-CSF], or recombinant erythropoietin) within 4 weeks prior to study treatment.
- 3.3.15 Patient with active interstitial lung disease (ILD)/pneumonitis or a prior history of ILD/pneumonitis requiring treatment with steroids
- 3.3.16 Patient has received prior treatment with PD-1, PD-L1 or PD-L2 inhibitor.

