4.3 Patient Registration

4.3.1 OPEN / IWRS

The Oncology Patient Enrollment Network (OPEN) is a web-based registration system available on a 24/7 basis. OPEN is integrated with CTSU regulatory and roster data and with the Lead Protocol Organization (LPOs) registration/randomization systems or Theradex Interactive Web Response System (IWRS) for retrieval of patient registration/randomization assignment. OPEN will populate the patient enrollment data in NCI's clinical data management system, Medidata Rave.

Requirements for OPEN access:

- A valid CTEP-IAM account.
- To perform enrollments or request slot reservations: Be on an LPO roster, ETCTN Corresponding roster, or Participating Organization roster with the role of Registrar. Registrars must hold a minimum of an AP registration type.
- If a DTL is required for the study, the registrar(s) must hold the OPEN Registrar task on the DTL for the site.
- Have an approved site registration for a protocol prior to patient enrollment.

To assign an Investigator (IVR) or Non-Physician Investigator (NPIVR) as the treating, crediting, consenting, drug shipment (IVR only), or receiving investigator for a patient transfer in OPEN, the IVR or NPIVR must list the IRB number used on the site's IRB approval on their Form FDA 1572 in RCR. If a DTL is required for the study, the IVR or NPIVR must be assigned the appropriate OPEN-related tasks on the DTL.

Prior to accessing OPEN, site staff should verify the following:

- Patient has met all eligibility criteria within the protocol stated timeframes, and
- All patients have signed an appropriate consent form and HIPAA authorization form (if applicable).

Note: The OPEN system will provide the site with a printable confirmation of registration and treatment information. Please print this confirmation for your records.

Access OPEN at <https://open.ctsu.org> or from the OPEN link on the CTSU members' website. Further instructional information is in the OPEN section of the CTSU website at

<https://www.ctsu.org> or <https://open.ctsu.org>. For any additional questions, contact the CTSU Help Desk at [name] or [contact].

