7.4 Routine Adverse Event Reporting

All Adverse Events **must** be reported in routine study data submissions. **AEs reported expeditiously through CTEP-AERS must also be reported in routine study data submissions.**

Adverse event data collection and reporting, which are required as part of every clinical trial, are done to ensure the safety of patients enrolled in the studies as well as those who will enroll in future studies using similar agents. AEs are reported in a routine manner at scheduled times during the trial using Medidata Rave. For this trial the Adverse Event CRF is used for routine AE reporting in Rave.

Symptomatic Adverse Events reported by patients through PRO-CTCAE are not safety reporting and may be presented with other routine AE data.

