11.1.2 Definitions

11.1.2.1 Evaluable for Toxicity

All patients will be evaluable for toxicity from the time of their first treatment with anetumab ravidansine and pembrolizumab or pembrolizumab.

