13.3 Sample Size/Accrual Rate

13.3.1 Sample Size

The phase 1 safety lead-in is expected to require a minimum of 12 patients and a maximum of 24 patients. The randomized phase 2 portion of this study is expected to require a minimum of 50 and a maximum of 98 evaluable patients. We anticipate accruing an additional 12 patients during the phase II portion of the trial to account for ineligibility, cancellation, major treatment violation, or other reasons. Therefore, the phase II portion is expected to accrue a maximum of 110 patients and overall sample size will be a maximum of 134 patients.

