13.7.3 Phase 2 Adverse Event Stopping Rule

The stopping rule applies to each group independently.

The stopping rule specified below is based on the knowledge available at study development. We note that the rule may be adjusted in the event of either (1) the study re-opening to accrual or (2) at any time during the conduct of the trial and in consideration of newly acquired information regarding the adverse event profile of the treatments under investigation. The study team may choose to suspend accrual because of unexpected adverse event profiles that have not crossed the specified rule below.

Accrual will be temporarily suspended to both groups if at any time we observe events considered at least possibly related to study treatment (i.e., an adverse event with attribute specified as “possible,” “probable,” or “definite”) that satisfy either of the following:

- if 4 or more patients in the first 20 treated patients in either group experience a grade 4 or higher non-hematologic adverse event at least possibly related to treatment.
- if after the first 20 patients have been treated, 25% of all patients in either group experience a grade 4 or higher non-hematologic adverse event at least possibly related to treatment.

We note that we will review grade 4 and 5 adverse events deemed “unrelated” or “unlikely to be related”, to verify their attribution and to monitor the emergence of a previously unrecognized treatment-related adverse event.

After consideration by the Principal Investigator and the statisticians and consultation with CTEP and CIRB, a decision will be made as to whether and how the study will proceed.

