13.8.2 Evaluation of Response

All patients included in the study must be assessed for response to treatment, even if there are major protocol treatment deviations or if they are ineligible. Each patient will be assigned one of the following categories: 1) complete response, 2) partial response, 3) stable disease, 4) progressive disease, 5) early death from malignant disease, 6) early death from toxicity, 7) early death because of other cause, or 9) unknown (not assessable, insufficient data). [Note: By arbitrary convention, category 9 usually designates the “unknown” status of any type of data in a clinical database.]

All of the patients who met the eligibility criteria (with the possible exception of those

who received no study medication) should be included in the main analysis of the response rate. Patients in response categories 4-9 should be considered to have a treatment failure (disease progression). Thus, an incorrect treatment schedule or drug administration does not result in exclusion from the analysis of the response rate. Precise definitions for categories 4-9 will be protocol specific.

All conclusions should be based on all eligible patients. Sub analyses may then be performed on the basis of a subset of patients, excluding those for whom major protocol deviations have been identified (*e.g.*, early death due to other reasons, early discontinuation of treatment, major protocol violations, etc.). However, these sub analyses may not serve as the basis for drawing conclusions concerning treatment efficacy, and the reasons for excluding patients from the analysis should be clearly reported. The 95% confidence intervals should also be provided.

REFERENCES

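### Section 13.5.4 restricts the phase 2 adverse-event tables and the between-arm grade 3+ test to eligible treated patients, while 11.1.2.1 counts every treated patient for toxicity.

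*Combined protocol and SAP*

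**What the plan says.** Section 13.5.4 defines who counts for adverse-event rates: "All eligible patients that have initiated treatment will be considered evaluable for assessing adverse event rate(s"). The same paragraph then specifies the maximum-grade frequency tables for each arm and a chi-square or Fisher test between the two groups for related grade 3 or higher events. It does not name phase 2, but arms and a two-group comparison exist only in the randomized part.

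Section 11.1.2.1 is wider: "All patients will be evaluable for toxicity from the time of their first treatment", with either the combination or pembrolizumab alone, and with no eligibility condition.

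Other sections bear on the point:

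- Section 13.2.1 counts for phase 1 toxicity everyone who received any amount of the combination.
- Section 13.7.3 bases the phase 2 stopping rule on treated patients: "if 4 or more patients in the first 20 treated patients in either group experience a grade 4 or higher non-hematologic adverse event" and the event is at least possibly related.
- Section 13.3.1 allows for "accruing an additional 12 patients during the phase II portion of the trial to account for ineligibility" and other losses.
- Section 13.8.2 says that all patients in the study "must be assessed for response to treatment, even if there are major protocol treatment deviations or if they are ineligible".

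**The concern.** The two definitions differ by exactly one group: patients who received study drug and were afterwards found ineligible. Section 11.1.2.1 counts their toxicity and 13.5.4 removes it.

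Leaving them out need not be neutral, because some eligibility criteria exist to limit toxicity. Section 3.3.12, for example, excludes corneal epitheliopathy on the ground that anetumab ravtansine "may worsen this condition and reduce vision". A dosed patient who breached such a criterion may be at higher risk of the very event being tabulated, and dropping that patient could lower the combination-arm rate. Section 7.4 gives the purpose of adverse-event data as "to ensure the safety of patients enrolled in the studies as well as those who will enroll in future studies" with similar agents, and a summary that omits exposed patients serves that purpose less well.

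What is at stake is limited to the final tables and one secondary comparison. With two definitions in the protocol, there is also room to choose the safety denominator after the data are known.

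**Working it through.** **Step 1: the definitions side by side.**

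| Section | Use | Must be treated? | Must be eligible? |
|---|---|---|---|
| 11.1.2.1 | Evaluable for toxicity | Yes | No |
| 13.2.1 | Phase 1 toxicity | Yes | No |
| 13.7.3 | Phase 2 stopping rule | Yes | No |
| 13.5.4 | Phase 2 tables and grade 3+ test | Yes | **Yes** |
| 11.1.2.2 and 13.1.2 | Tumor response | Yes | Yes |

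Section 11.1.2.2, which directly follows 11.1.2.1, states eligibility explicitly for response. Its absence from 11.1.2.1 therefore reads as a real difference. Section 13.5.4 is the only safety definition that carries the eligibility condition. The stopping rule is a monitoring rule on a different endpoint (related grade 4 or higher non-hematologic events), so it shows the protocol's usage but does not settle the analysis set.

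**Step 2: how many patients could be affected.** Inputs from 13.3.1: 98 evaluable patients and an allowance of 12. The plan's own total reproduces: 98 + 12 = 110. The 12 cover ineligibility, cancellation, major treatment violation and other reasons together, so the planned number of treated but ineligible patients lies between 0 and 12.

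- 1/110 = 0.9%
- 3/110 = 2.7%
- 6/110 = 5.5%
- 12/110 = 10.9%

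**Step 3: arithmetic limits on one arm's rate.** Assumptions: 55 treated in the combination arm (half of 110, everyone treated) and 8 with a grade 3+ event, so 8/55 = 14.5%. This is close to the 15% that 13.1.3.2 uses as a hypothetical event rate. If k patients are dropped, the reported rate runs from (8 − k)/(55 − k), where all of them had an event, to 8/(55 − k), where none did.

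| k dropped | Lowest | Highest |
|---|---|---|
| 1 | 7/54 = 13.0% | 8/54 = 14.8% |
| 3 | 5/52 = 9.6% | 8/52 = 15.4% |
| 6 | 2/49 = 4.1% | 8/49 = 16.3% |

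These are logical limits, not forecasts.

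**Step 4: expected shift under unequal risk.** Assumptions: risk 15% in eligible and 30% in ineligible patients, again with 55 treated. The expected all-treated rate is [(55 − k) × 0.15 + k × 0.30]/55, against 15.0% under 13.5.4.

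| k ineligible | All-treated rate | 13.5.4 is lower by |
|---|---|---|
| 1 | 8.40/55 = 15.27% | 0.3 points |
| 3 | 8.70/55 = 15.82% | 0.8 points |
| 6 | 9.15/55 = 16.64% | 1.6 points |

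At equal risk the expected shift is 0 for any k.

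**The case against.** The case against giving this much weight has five parts.

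- **Little depends on this set.** The events are still reported (7.4), safety data still go to the monitoring board (13.7.1), and qualifying events still count toward the stopping rule (13.7.3). The between-arm test has no stated alpha, power or decision rule, and adverse events are not among the secondary objectives in 1.2. This stands, and it is why the point is confined to the final summary.
- **Few patients should be affected.** Before registration, sites verify: "Patient has met all eligibility criteria within the protocol stated timeframes". The study calendar also requires an eye examination with slit lamp in all patients within 28 days before the first dose, so the corneal example is one of the less likely late findings. This stands as to frequency. The example shows only that some criteria are tied to toxicity, and the direction of any bias is possible rather than demonstrated.
- **The figures rest on assumptions.** The 55 treated, the 8 events and the 30% risk are not forecasts from the protocol. The 4.1% limit needs all six dropped patients to have had an event; at 30% risk each, that has probability 0.3^6 = 0.07%. The expected shifts of 0.3 to 1.6 points compare with a standard error of √(0.15 × 0.85/55) = 4.8 points. Ineligible patients would also be expected in both arms, so the comparison may move less than a single arm's rate. All of this stands.
- **Section 13.8.2 bases all conclusions on eligible patients.** That sentence falls under evaluation of response. It suggests a house convention but does not address adverse events, so it does not reconcile 13.5.4 with 11.1.2.1.
- **A population of patients given any study drug is not word for word that of 11.1.2.1,** which names treatment with the combination or with pembrolizumab. A combination-arm patient who received only the first infusion is not literally covered there. This is a small drafting gap and does not make the change unsound.

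**Conclusion.** The concern holds. The inconsistency is certain on the text, and 13.5.4 is the definition that departs from the protocol's other safety passages. Followed as written, it removes dosed patients from the trial's planned summary of what the combination adds in toxicity.

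The size cannot be computed, because the documents give no count of treated but ineligible patients. The planning bound is 0 to 12 of 110. Under the assumed 15% and 30% risks the expected understatement in the combination arm is 0.3 to 1.6 points for 1 to 6 such patients; it is nil at equal risk or if no such patients occur. The effect is probably modest, but the remedy costs almost nothing, so the change should be made before the analysis.

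**What to change.** In 13.5.4, replace the eligible-and-treated population with *all patients who received any study drug*, in line with 11.1.2.1, and apply it to both the frequency tables and the grade 3+ comparison. Using the same phrase in 11.1.2.1 would close the small gap over a patient given only the first infusion. Leave the response-rate population in 13.1.2 unchanged.

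The essential change is one phrase. It adds no patients, visits or data, because 7.4 already requires all adverse events to be reported. No sample size, boundary or power figure changes.
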